## Design

Pragmatic group randomized trial of PACT teams (n=39 teams recruited, estimated 24 at DVAHS and 15 at Richmond VAMC) will be randomized into 2 groups: a control group (no additional support, and a centralized Bone Health Service (BHS) model. Outcomes for all patients eligible for osteoporosis screening within the randomized PACTs will be assessed by investigators masked to group assignment via EHR at baseline and 2 years. Outcomes for PACT providers will be assessed using qualitative methods (nominal group technique).

**Outcome measures** are listed in the table 1 below.

Table 1. Outcome measures by Aim. RDW=Regional Data Warehouse; MPR=Medication Possession Ratio; FRAX=Fracture Risk Assessment Tool.

Outcome	Definition/Measure	Data Source/Timing	Important Difference
Patient (Panel) Level (Aim 1)			
Screening Rates	Proportion of eligible men screened in last 12 months	RDW at baseline, year 1 and year 2	25% increase from 6% Control
Medication Initiation	Proportion of screened men meeting treatment threshold (T score $\leq -2.5$ or FRAX score high-risk) who receive at least 1 prescription	RDW, intervention period year 1 and year 2, non-VA medication lists by chart abstraction.	30% increase from 55% Control
Medication Implementation	Days of medication dispensed divided by follow-up days	Pharmacy dispensing records, for patients started within prior year at baseline, year 1 and 2. Non-VA medication lists by chart abstraction.	20% increase in MPR $>80\%^{14}$ from 30% Control
Medication Discontinuation	Time between first prescription dispensing date and the date of first medication possession gap of $\geq 3$ months	Pharmacy dispensing records, for patients started within prior year at baseline, year 1 and 2. Non-VA medication lists by chart abstraction.	20% difference
Bone Mineral Density	BMD g/cm  at femoral neck and lumbar spine in random sample of men eligible for screening	Random sample of 712 men (356 UC, 178 each of the other 2 models) eligible for screening in panel at least 1 year, measured 2 years after start date	Post-intervention between group difference of 3% femoral neck, 5% lumbar spine 
Harms	Proportion of men started on oral medication for new GI distress in 3 months  Subtrochanteric fractures or Osteonecrosis of the jaw	RDW ICD10 codes, new prescription for proton pump inhibitor or H2 blocker.  RDW ICD10 codes	15% increase from 30% Control  >expected 1/50,000 patient years treatment

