Aim 3. Prior Markov models of osteoporosis screening have been adapted for this study (Figure 6). A Markov cost-utility model with 6 health states will be constructed comparing 3 different strategies of DXA screening, followed by 5 years of treatment with alendronate (the most commonly prescribed medication) for those with a femoral neck T-score of  $<-2.5$  or FRAX 10 year fracture risk above current treatment thresholds (3% hip, 20% major osteoporotic fracture). For the base-case analyses, the model will be run for five different starting ages (65, 70, 75, 80, and 85) using Monte Carlo simulations with 40,000 trials each. Running the models for 5-year increments allows us to adjust the transition probabilities for observed differences over time (e.g., higher fracture rates or different adherence rates with older age). The health states in the model are no fracture, post distal forearm fracture, post clinical vertebral fracture, post hip fracture, post other fractures (humerus, scapula, ribs, pelvis, distal femur, pelvis, patella, tibia, or proximal fibula), and death. Following the recommendations of the 2nd Panel on Cost-

Table 5. Data Sources for Aim 3 (see also Health Systems Policy Outcomes Section)

Data Category	Source(s)
Proportion screened and treated	Aggregated aim 1 results
Medication adherence, persistence	Aggregated aim 1 results
Bone Mineral Density	Random sample of 712 men (356 UC, 178 each of the other 2 models) eligible for screening in panel at least 1 year, measured 2 years after start date
Treatment efficacy	Published efficacy for bisphosphonates by medication adherence and persistence rates
Fracture rates	National VA data (preliminary results)
Fracture costs	National VA and CMS data including Fee Basis and CHOICE costs (preliminary results)
Screening and Treatment costs	Aim 2 results, current VA/CMS DXA cost, rare serious harm estimates from population data
Fracture disutility	Systematic review of disutility by fracture type

Effectiveness in Health and Medicine, we will analyze our model from both the VA and societal perspectives and present our results as an impact inventory.

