The direct and indirect costs of that fracture will be assigned as a transition cost. The disutility associated with these fractures will be modeled as a QALY decrement associated with that fracture state based on a published systematic review of fracture disutility rates and is assigned for 6 months upon which they return to baseline state, except for hip and vertebral fractures for which permanent disutility is the norm. If an individual suffers an additional fracture, the costs of that fracture are assigned, but the person remains in the post vertebral or post hip fracture state because the long-term disutility associated with prior vertebral and hip fractures is greater. Long-term care costs beyond the first year after hip fracture are assigned as a cost per year. Individuals in the model will be eligible (at risk) of transition to a different state once every 3 months, and a maximum of 2 fracture types is assumed. We will parameterize our model using inputs derived from Aims 1 and 2 of the current grant and from the published literature. A discount rate of 3% will be assumed for costs and health benefits.

Treeage software will be used for analyses. One-way sensitivity analyses will be performed varying discount rates, fracture rates, fracture costs, fracture disutility, costs of DXA, the onset

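### Aim 3 specifies a QALY loss for fractures but none for drug harm, and any uncounted drug-related loss would fall mainly on the BHS arm

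*Protocol*

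**What the plan says.** The model is described under Aim 3 in the Protocol's Data Analysis and Statistical Considerations. The Aim 3 text in the body of the SAP reads the same on these points.

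- **States.** "The health states in the model are no fracture, post distal forearm fracture, post clinical vertebral fracture, post hip fracture, post other fractures", and death. None represents a treatment harm.
- **Utility.** "The disutility associated with these fractures will be modeled as a QALY decrement associated with that fracture state". It lasts six months, or permanently for hip and vertebral fractures. The only disutility source in Table 5 is "Systematic review of disutility by fracture type".
- **Drug harm.** It appears once in Table 5, in the row for screening and treatment costs: "Aim 2 results, current VA/CMS DXA cost, rare serious harm estimates from population data".
- **Sensitivity analyses.** The one-way list includes fracture disutility, adherence and several costs. It names no harm rate, harm cost or harm disutility. The two-way analyses test reduced drug efficacy.

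Table 1 (Design section) lists a GI harm among the Aim 1 outcomes, "Proportion of men started on oral medication for new GI distress in 3 months", with a planning difference of "15% increase from 30% Control". The cost-effectiveness row of that table says the Markov model uses the outcomes above it, together with quality-of-life values from VA and published sources. The Aim 3 text adds that inputs will come from Aims 1 and 2 and the literature.

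**The concern.** The model follows five years of alendronate, an oral drug. The trial measures GI distress after oral starts, and the BHS Adherence Promotion section uses GI distress as its example of an adherence barrier. The plan thus anticipates this harm and collects data on it, yet the detailed model specification gives it no way to reduce QALYs.

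The gap is not neutral between arms. BHS is designed to screen and treat many more men. If fractures prevented are credited and quality of life lost to treatment is not charged, the arm that treats more is favoured. Aim 3 is meant to inform policy through the probability, set at above 80%, that cost per QALY meets stated thresholds. The QALY gain per treated man is small, so a reader needs to know whether that statement survives when drug harm is counted.

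**Working it through.** The plan states no cost per QALY, baseline utility or GI disutility, so there is no figure to reproduce. What can be checked is the direction, from the plan's inputs, and the possible size, from labelled assumptions.

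**1. Share of eligible men treated** = screened × meeting threshold × initiating. Inputs are from Protocol Tables 1 and 6.

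- Control: 0.06 × 0.25 × 0.55 = 0.00825, or 0.8%.
- BHS, low: 0.31 × 0.25 × 0.715 = 0.0554, or 5.5%. This takes Table 1's 25% screening increase as percentage points and the 30% initiation increase as relative (0.55 × 1.30).
- BHS, high: 0.40 × 0.25 × 0.85 = 0.085, or 8.5%. This takes Table 6's 40% screened and the 30% as percentage points.
- Ratios: 0.0554/0.00825 = 6.7 and 0.085/0.00825 = 10.3.

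Reading the 25% as relative would give 0.06 × 1.25 = 7.5% screened, which cannot be squared with the 40% in Table 6.

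**2. QALY loss per starter** = new GI distress × drug-attributable share × disutility × duration. The 30% is Table 1's control planning rate for any new GI distress. Assumed: 10 to 100% attributable, disutility 0.02 to 0.10, duration 0.25 year.

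- Low: 0.30 × 0.10 × 0.02 × 0.25 = 0.00015.
- High: 0.30 × 1.00 × 0.10 × 0.25 = 0.0075.

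**3. Fracture gain per starter** = rate × 5 years × relative reduction × QALY per fracture × persistence. The rate of 2.5 per 100 person-years is from Table 1. The reductions of 16% (other non-vertebral) to 45% (vertebral) are from the Background. Assumed: 0.05 to 0.5 QALY per fracture, 50 to 100% persistence.

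- Low: 0.025 × 5 × 0.16 × 0.05 × 0.5 = 0.0005.
- High: 0.025 × 5 × 0.45 × 0.5 × 1.0 = 0.028.

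**4. Loss as a fraction of gain.**

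- Smallest: 0.00015/0.028 = 0.5%.
- Largest: 0.0075/0.0005 = 15 times the gain.
- One intermediate case: half attributable and disutility 0.02 give a loss of 0.30 × 0.5 × 0.02 × 0.25 = 0.00075. With 0.2 QALY per fracture and full persistence, the gain is 0.004 at a 16% reduction (ratio 19%) and 0.01125 at 45% (ratio 7%).

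The extremes stack every assumption in one direction. They show only that the inputs do not settle the matter.

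**5. Rare serious harms.** Table 1 gives an expected rate of 1 per 50,000 treated patient-years. Over five years that is 5/50,000 = 0.0001 events per starter. At an assumed 0.5 QALY per event the loss is 0.00005, below the lowest GI value above. A decrement here is for completeness; the GI term carries the uncertainty.

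**The case against.** The strongest reply is that exclusion is not shown. Table 1 says the listed outcomes feed the model, harms are one of them, and the Aim 3 text draws inputs from Aims 1 and 2. Table 5 is a list of data sources and is not exhaustive: it has no row for mortality, baseline utility or long-term care cost. It also refers to a policy-outcomes section that is not in the text available for review, and the model figure is not shown. This stands, to the extent that a reader should not infer that GI harm has been decided out of the model. It does not close the gap. A GI rate alone cannot change QALYs, and the only disutility source named is by fracture type. Nor is the Table 1 line a literal input list, since fractures are also an outcome above it, yet fracture rates are taken from national VA data.

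A reader might also take 30% as the GI harm of treatment. The documents do not support that. It is a control-arm planning rate for new GI distress among oral starters, detected by diagnosis codes or a new acid-suppressant prescription. No untreated background rate is given.

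A reader might pick middle values and infer that about half the fracture gain is lost: 0.15 × 0.05 × 0.25 = 0.0019 against 5 × 0.025 × 0.28 × 0.10 = 0.0035. Every GI and QALY value there is assumed. With 0.5 QALY per fracture the gain is 0.0175 and the ratio about 11%. The gain may be understated too: treated men are selected for high risk, hip and vertebral disutility is permanent, and hip fracture carries excess mortality.

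Two further points have partial force. GI-driven stopping already lowers BHS benefit through the adherence and persistence inputs, but that charges nothing for the symptoms themselves. The mortality benefit claimed for bisphosphonates in the Background is not listed in Table 5 either, and that omission works against BHS. The probabilistic analysis is said to draw every parameter, but it cannot draw one the model does not contain.

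**Conclusion.** The point holds as a gap in specification with a predictable direction. As written, Aim 3 assigns a QALY decrement to fractures only, enters rare serious harms as a cost, and states no cost, disutility or sensitivity analysis for the GI harm that Aim 1 measures. Because BHS is planned to treat about 7 to 10 times as many eligible men, any uncounted drug-attributable loss falls mainly on BHS and flatters its cost per QALY.

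The direction rests on two conditions: that some GI distress is caused by treatment, and that the planned screening and initiation rates are roughly met. The size is not fixed by the documents and could be negligible or material. The evidence does not establish that the Aim 3 conclusion is wrong, nor that all omissions taken together favour BHS. Nothing in the Aim 1 or Aim 2 comparisons is affected.

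**What to change.** Before the model is run:

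1. Reconcile Table 1 with Table 5, stating whether and how the Aim 1 harms enter.
2. Add a GI event in treated men, with a short-term disutility and a cost. The Table 1 window and the model cycle are both three months, so it fits the existing structure. Its probability should be a drug-attributable excess, from the literature or from Aim 1 data net of a background rate. The raw Aim 1 rate by arm should not be used: it is measured only in starters, so it would charge background distress to treatment. The control estimate would also rest on few men, 20 teams × 100 × 0.06 × 0.25 × 0.55 = 16.5 per screening year.
3. Give the rare serious harms a QALY decrement as well as a cost.
4. Vary these terms in the one-way and probabilistic analyses, and report cost per QALY and the probability at each threshold with and without them.

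The cost is a few extra parameters, mostly from the literature, in a desk model, with no change to treatment, visits or sample size. The resulting cost per QALY may be less favourable, and the attributable GI rate will itself be uncertain.

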Screening Tool calculation. We do not expect attrition as new patients are added as others leave with relatively constant panel size. Finally, we determine power for the single degree of freedom contrast of import – Usual Care vs. BHS groups across the follow-up time points. For each of the individual outcomes, assumptions and power requirements are listed in the Table. A sample size of 39 PACTs (19 BHS vs. 20 Usual Care) with an average 100 patients / PACT provides over 85% power for all our primary patient-level outcomes, except fracture rates - an exploratory analysis.

Table 6. Power calculation assumptions for Aim 1

Outcome	Assumptions, Minimal Clinically Significant Difference	Power for 39 PACTs and 3900 patients
Screening Rates (PACT level)	6% Usual Care, 40% new models	>0.99
Osteoporosis Treatment	Assume 25% of screened meet treatment thresholds. 30% increase from 55% Usual Care	>0.99
Medication Adherence	Usual Care MPR 0.60 (SD 0.35). 20% increase	0.85
Bone Mineral Density (BMD) Femoral Neck in random sample of high-risk patients	0.939 g/cm  in BHS group vs. 0.967 Usual Care with SD pooled =0.133	0.90 for random sample of 952 patients (25/team); 0.80 for 712 (19/team)

**Missing data Strategies.** As is standard in administrative databases, the absence of a diagnosis code (e.g., fracture) will be assumed to indicate that the event did not occur, and coded by default as 'not present'. For continuous measures where zero is illogical, we will impute a value, simulate and use bootstrapping to derive estimates of effect with appropriate standard errors. To implement the multiple imputation techniques for primary analyses, we will use preliminary analyses of such associations, including graphical displays, to investigate the plausibility of the assumptions underlying the imputation model employed. Further, we will use 25 or more imputed data sets, with FU bootstrapped estimates in order to reduce the impact of the random sampling.

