### **Specific aims:**

1. Compare the impact of BHS primary osteoporosis screening models on **patient level outcomes** strongly associated with fractures as measured by the EHR at 2 years; 1) eligible proportion screened; 2) medication adherence (initiation; implementation, and discontinuation); 3) bone mineral density at the femoral neck in a random sample of high risk patients. Fracture rates (fractures/patient years) are exploratory.

H1a: PACT teams randomized to BHS will have better patient level outcomes compared to usual care at pre-specified clinically important levels, adjusting for baseline levels.

2. Determine the impact of BHS primary osteoporosis screening models on **provider and facility level outcomes** including change in DXA volume, change in metabolic bone disease clinic volume (assessed by EHR), and PACT provider time and satisfaction (assessed by Nominal Group Technique).

H2a: DXA and metabolic bone disease clinic volumes will increase during the intervention, with a higher proportion of referrals coming from PACTs randomized to BHS.

H2b: Provider satisfaction with osteoporosis screening systems will be higher for PACTs randomized to BHS management compared to usual care.

3. Determine the impact of BHS primary osteoporosis screening programs on **health system and policy level outcomes** using Markov models of screening program cost per quality adjusted life year. Model inputs are based on VA national fracture data from our prior work, results from aims 1 and 2, and published quality of life estimates.

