propensity score matching) to make the groups conditionally equal. The parameter of interest will be the Group mean (and standard error) over time, and measured by the ‘average’ PACT value at each time point. Finally, we note that the estimation models above can be adapted to

outcomes distributed other than normal, including Poisson (for number of events/time) and binary (for binary events). This is a 2 group by 3

[figure not shown]

Figure 6. Markov model for Aim 3 analyses of economic impact of 3 screening models.

yearly time point design. To control the overall Type-I error level, we will use the baseline time point as a baseline covariate, and assess group differences at the following time points controlling for baseline. Level of statistical significance will be set at 0.05 (two-tailed) for all tests. In this work, we proposed a GroupxTime interaction, using the time effects as classes/factors. Depending on the significance of this omnibus test, we can assess tests of individual differences (say, group differences at a specific point) by gate-keeping strategy. In the case where the omnibus group by time interaction is significant, then, these will be done without a Type-I error penalty. Initially, we will assess a Time by Group interaction (on 1 degree of freedom). If that effect is declared statistically significant, we will perform follow-up tests to determine where the group differences exist at each follow-up time point, using the gate-keeping strategy listed above. If the Group by Time interaction is not significant, then the main effects of Group and Time will be tested.

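### The claim of over 85% power for all primary patient-level outcomes takes in medication discontinuation, which has no power row, control rate or effect scale and falls short on the starter numbers that Table 6 implies

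*Protocol*

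**What the plan says.** Aim 1 in the protocol's Specific aims (repeated in the SAP's Revised Specific Aims) names "medication adherence (initiation; implementation, and discontinuation" as patient-level outcomes and calls only fracture rates exploratory. Table 1 of the Design section defines discontinuation as "Time between first prescription dispensing date and the date of first medication possession gap" of at least 3 months. It gives the important difference as 20%, without saying whether that is absolute, relative or a hazard reduction.

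The protocol's Power text and the SAP's Revised Analysis Plan then make two statements. First, "For each of the individual outcomes, assumptions and power requirements are listed in the Table". Second, the planned 39 teams (19 in BHS and 20 in usual care, at about 100 men each) are said to give a design that "provides over 85% power for all our primary patient-level outcomes, except fracture rates - an exploratory analysis". The table that follows (Table 6 in the protocol) has four rows: screening, osteoporosis treatment, medication adherence as a mean medication possession ratio (MPR), and BMD. The SAP's older three-arm power table adds a fracture row but has none for discontinuation either.

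The analysis text for Aims 1 and 2 restricts adherence analyses to men who were screened, had a low DXA value and were prescribed treatment. On testing it says: "Level of statistical significance will be set at 0.05 (two-tailed) for all tests".

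**The concern.** The power statement excepts fractures and nothing else, so a reader will take it to cover discontinuation, yet nothing in either document supports a figure for that outcome. The mean-MPR row cannot stand in for it: one is a continuous average, the other a time to event, and no control rate is supplied to link them.

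The denominator is also small. The 3,900 patients in the table heading are not the men at risk of discontinuing; only starters are, and few are expected in usual care, where screening is 6%. The BHS follow-up calls and refill checks aim directly at discontinuation, and persistence is an input to the Aim 3 model. A null result could be read as evidence of no effect because the plan says the outcome was well powered.

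**Working it through.** **Inputs from the documents.** Two-sided alpha 0.05. Usual care 20 × 100 = 2,000 patients; BHS 19 × 100 = 1,900. Screening 6% and 40%; 25% of those screened meet the treatment threshold; initiation 55% in usual care, and 85% in BHS if the 30% increase is absolute. Table 1 defines screening as a 12-month proportion.

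**Inputs not in the documents.** Control discontinuation is assumed at 40–80%. How screening accumulates over two years is also assumed.

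**The plan's own figures first.**
- BMD, difference 0.967 − 0.939 = 0.028, SD 0.133: power = Φ(0.028 / (0.133√(2/n)) − 1.96). With n = 476 per arm this is 0.901; with 356 it is 0.802. Both reproduce.
- Screening reproduces at >0.99, even at an ICC of 0.1.
- Treatment initiation, 55% to 85%: 0.94 with one pass of eligible men (30 vs 190) and 0.998 if both arms double (60 vs 380), against >0.99 stated.
- Mean MPR, absolute gain 0.20, SD 0.35: 0.60 at 16.5 vs 161.5 starters, 0.849 at 33 vs 161.5 and 0.878 at 33 vs 323, against 0.85 stated.
- Discontinuation: there is no figure to reproduce.

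**Starters.**
- Usual care: 2,000 × 0.06 × 0.25 × 0.55 = 16.5 in one pass; 33 if the 6% recurs in a second year.
- BHS: 1,900 × 0.40 × 0.25 × 0.85 = 161.5 if 40% is the total; 323 if it recurs.
- Reading the initiation increase as relative (71.5%) gives 135.9 BHS starters in one pass and changes little, because the usual-care count is the limit.

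**Formulas.**
- Log-rank: Φ(|ln HR| / √(1/e₁ + 1/e₂) − 1.96), where e₁ and e₂ are events per arm. For an absolute difference, HR = ln(1 − pT)/ln(1 − pC); for HR 0.8, pT = 1 − (1 − pC)^0.8.
- Two proportions: once with pooled variance, and once with unpooled variance and a t reference on 39 − 2 = 37 df.
- Ceiling for HR 0.8 if all N starters stop: Φ(|ln 0.8| √(N·a(1 − a)) − 1.96), with a the usual-care share.

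**Example.** 40% vs 20% gives HR = ln 0.8 / ln 0.6 = 0.437 and |ln HR| = 0.828. At 33 vs 161.5 starters, events are 13.2 and 32.3, the standard error is 0.327 and power is Φ(2.535 − 1.96) = 0.72. At 16.5 vs 161.5, events are 6.6 and 32.3, the standard error is 0.427 and power is 0.49.

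**Results, control discontinuation 40–80%, no clustering.**

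| Starters (usual care vs BHS) | 20 points, log-rank | 20 points, pooled proportions | 20 points, 37 df | HR 0.8, log-rank | HR 0.8 ceiling |
|---|---|---|---|---|---|
| 16.5 vs 161.5 | 0.40–0.49 | 0.33–0.47 | 0.33–0.45 | 0.08–0.12 | 0.14 |
| 33 vs 161.5 | 0.62–0.73 | 0.56–0.68 | 0.54–0.69 | 0.11–0.18 | 0.21 |
| 33 vs 323 | 0.68–0.78 | 0.60–0.72 | 0.57–0.74 | 0.12–0.19 | 0.23 |

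Simulated log-rank tests (4,000 runs, control 40–70%) agree: 0.42–0.52 in one pass and 0.64–0.74 over two years for 20 points, and 0.11–0.20 for HR 0.8. A proportional cut of 20% is smaller than 20 points at any control rate below 100%, so it has less power than the absolute reading. An ICC of 0.1 lowers the pooled-proportions range at 33 vs 161.5 (control 40–70%) from 0.56–0.68 to 0.49–0.60.

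**What 85% would need.** For HR 0.8, events = (1.96 + 1.036)² / (a(1 − a)(ln 0.8)²): about 1,280 at 33:161.5 and 2,144 at 33:323, against 195 and 356 starters. For an absolute 20 points, log-rank power is 0.86 at a 30% control rate with 33 vs 161.5, and 0.85 at 35% with 33 vs 323. The pooled-proportions test needs a lower rate: 0.81–0.85 at 30% and 0.89–0.92 at 25%. In one pass, log-rank power is still 0.81 at 25%.

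**The case against.** No passage lists which outcomes are primary. Aim 1 treats medication adherence as one numbered item with three parts, and Table 6's adherence row could be meant to represent all three. That stands as far as it goes: including discontinuation is an inference, drawn from Aim 1 and from fractures being the only exception. But the plan also says every individual outcome is in the table, and Table 1 gives discontinuation its own definition and its own important difference.

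A reader might infer from the near match at 33 vs 161.5 starters (mean MPR 0.849 against 0.85) that these are the sponsor's own denominators. The documents do not support this. Neither count appears in them, and the pair doubles usual-care screening while leaving BHS at a single 40%. The 0.85 and >0.99 entries also stand unchanged in the SAP's older table, which was built for 36 teams, 2,376 patients and 70% screening. There the same chain gives 792 × 0.06 × 0.25 × 0.55 ≈ 6.5 usual-care starters and MPR power of about 0.30. The match may be coincidence.

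A reader might also see a contradiction in the BMD row, which shows 0.80 at 712 men. The plan discloses that beside the claim as a fallback from 952, so it is a matter of loose wording.

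Finally, nothing says a null result would be read as no effect, and the plan will report standard errors. That limits the consequence but does not support the stated power.

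**Conclusion.** The point holds in this form. The gap in the text needs no assumption: an Aim 1 outcome falls under a blanket power claim with no row, control rate or effect scale behind it.

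The size of the shortfall does rest on assumptions: the chain of rates in Table 6, control discontinuation of 40–80%, and either one pass or two years of accrual. Within these, no reading of the 20% difference reaches 85%, and clustering would lower the figures further.

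The documents do not support saying that 85% is out of reach on every reading. With two-year accrual, an absolute scale and control discontinuation of about 30–35% or lower, a log-rank test gets there; a pooled test of proportions needs a rate nearer 25–30%. Such rates sit poorly with Table 1, where only 30% of controls are expected to have an MPR above 80%, but they are not excluded. Nor do these figures show that discontinuation must become a secondary endpoint; that is a design choice.

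**What to change.** In the protocol's Power text and the SAP's Revised Analysis Plan, limit the power sentence to the outcomes and sample sizes that the table shows. Adherence is 0.85, not over it; BMD is 0.90 at 952 men and 0.80 at 712.

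Add a discontinuation row that states the scale of the 20% difference, the assumed control rate, the expected starters per arm and the resulting power. These should be the sponsor's own inputs, labelled as assumptions, not the ranges used here. Report discontinuation with a confidence interval and without a claim of adequate power.

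The cost is one sentence in two places and one table row, and a stated figure becomes less favourable. Enrolment, procedures and the endpoint's standing do not change.

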Osteoporosis Treatment	25% of screened meet treatment thresholds. 30% increase from 55% Usual Care	306 patients (102/arm)	>0.99
Medication Adherence	Usual Care MPR 0.60 (SD 0.35). 20% increase new models	1680 patients (560/arm)	0.85
Fractures (exploratory)	Usual Care 2.5 fractures/100 patient yrs (SD 0.2), 10% decreased hazard with new models	78,297 2175/arm	0.32

Once the data is coded, final analysis will proceed in 2 steps. **1) Generation of top 7 themes for each question.** Although each group responds to the same questions, because they work independently the number, wording and order of the statements will be different. Larger groups also have a wider score range than smaller groups. To address this issue we will use procedures described by van Breda to analyze data across groups. Using the coded data described above, we will calculate average scores for each theme by summing the total of statement scores for the theme divided by the number of statements in the theme. The top 7 themes will be listed for each question, along with exemplar statements. **2) Assessment of Implementation Variation.** We will examine variation in implementation by site and provider type in order to better inform dissemination. Co-occurrence tables and matrices of the themes identified through content analysis as described above will be generated by site characteristics (urban/rural, academic/community) and provider type (medical/RN). We will identify similarities and differences in the frequency of the themes, the ordering of the statements, and the discussion around the statements.

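### The power of more than 0.99 stated for treatment initiation is unsupported: the plan's own rates give about 30 to 60 usual-care men in the analysis, and the scale of the 30% increase is not stated

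*Protocol*

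**What the plan says.** Table 1 (protocol, Design) defines medication initiation as "Proportion of screened men meeting treatment threshold" who then receive at least one prescription. The data cover years 1 and 2 of the intervention. The same table defines the screening rate over a 12-month window.

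Table 6 (protocol, Power paragraph; repeated in the SAP's Revised Analysis Plan) has a column headed "Power for 39 PACTs and 3900 patients". Its screening row assumes "6% Usual Care, 40% new models". Its treatment row reads "Assume 25% of screened meet treatment thresholds. 30% increase from 55% Usual Care", with power above 0.99. The row gives no number of men entering the analysis, does not say whether the increase is relative or absolute, and gives no ICC. The Power text says only that the ICC is below 0.1.

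The text before the table takes 19 BHS and 20 usual-care teams, at 100 men per team on average, as its basis. Its conclusion is that this design "provides over 85% power for all our primary patient-level outcomes, except fracture rates".

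The SAP's superseded three-arm Table 6 gave "306 patients (102/arm") for 80% power on the same assumption. It does not say whether these are screened men or men at the treatment threshold.

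**The concern.** The power column is headed with all 3900 men, but most of them cannot enter this endpoint. In usual care the plan expects 6% to be screened and a quarter of those to meet the threshold, so the control group is a small fraction of its 2000 men. A figure above 0.99 is hard to square with that, and the row omits the inputs needed to check it.

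Initiation is one of the named Aim 1 patient-level outcomes, and the proportion treated feeds the Aim 3 economic model. If the comparison rests on a few dozen control men, a null result could be read as a negative finding from a test with near-certain power. That reading would be unjustified if the true power is around one half.

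**Working it through.** **Inputs.** Two-sided 0.05 ("Level of statistical significance will be set at 0.05 (two-tailed) for all tests"); 20 usual-care and 19 BHS teams of 100 men; screening 6% vs 40%; 25% of screened men at threshold; control initiation 55%. The increase is read as relative (55% × 1.30 = 71.5%, d = 0.165) or absolute (85%, d = 0.30). ICC 0 to 0.1 is an assumed range, since the plan says only below 0.1.

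**Reproducing the printed figure.** If every man is treated as screened, 25% gives 2000 × 0.25 = 500 and 1900 × 0.25 = 475. On the relative scale, SE = √(0.55×0.45/500 + 0.715×0.285/475) = 0.0304, and Φ(0.165/0.0304 − 1.96) = 0.9997. The absolute scale gives 1.00. Both ignore clustering and the screening rates in the row above.

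**Men expected from the plan's own rates.**
- Usual care: 2000 × 0.06 × 0.25 = 30, or 60 if 6% are screened in each of two years.
- BHS: 1900 × 0.40 × 0.25 = 190, or 380 if 40% are newly screened in each year. The 380 is generous, because the analysis section censors men once screened.

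**Power on those counts.** The unpooled version is Φ(d/SE₁ − 1.96). The pooled version is Φ((d − 1.96·SE₀)/SE₁), where SE₀ uses the pooled proportion. For 30 vs 190, relative, ICC 0:
- SE₁ = √(0.2475/30 + 0.2038/190) = 0.0966, and Φ(1.71 − 1.96) = 0.40.
- Pooled proportion (16.5 + 135.85)/220 = 0.6925, SE₀ = 0.0907, and Φ((0.165 − 0.1777)/0.0966) = 0.45.

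For clustering, each arm's count is divided by 1 + (m − 1)·ICC. Here m is 1.5 or 3 men per usual-care team and 10 or 20 per BHS team. At ICC 0.1 the divisors are 1.05, 1.2, 1.9 and 2.9.

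| Usual care vs BHS | Relative, ICC 0 | Relative, ICC 0.1 | Absolute, ICC 0 | Absolute, ICC 0.1 |
|---|---|---|---|---|
| 30 vs 190 | 0.40–0.45 | 0.36–0.39 | 0.89–0.94 | 0.85–0.90 |
| 60 vs 190 | 0.63–0.66 | 0.51–0.52 | 0.991–0.995 | 0.97 |
| 60 vs 380 | 0.68–0.72 | 0.53–0.56 | 0.994–0.998 | 0.97–0.98 |

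Each range runs from unpooled to pooled variance. With 190 BHS men and no clustering, power of 0.99 would need about 777 usual-care men on the relative scale and about 51 on the absolute scale.

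**Does the superseded 102 per arm reveal the scale?** That calculation compared usual care with the two models combined, so allocation was 1:2. For 80% power:
- Relative, unpooled: (0.2475 + 0.2038/2) × 7.849/0.165² = 100.7 threshold-meeting men per arm (98.1 pooled).
- Absolute, pooled: 25.3 threshold-meeting men per arm, and 25.3/0.25 = 101.2 screened men, rounded up to 102 (108.6 unpooled).

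Both readings fit, so the figure does not identify the scale.

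**The case against.** The strongest defence is the absolute reading. Table 1 expresses the screening target as a 25% rise from 6%. A relative rise would be 7.5%, which cannot be meant when Table 6 powers 6% against 40%. The initiation target has the same form. If it too is absolute, power lies between 0.85 and 0.998 across all the cases above, the over-85% sentence stands, and above 0.99 is right with 60 usual-care men and no clustering. This stands, and it means the printed figure cannot be called wrong outright.

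A reader might infer from 102 per arm that the increase is relative and that usual care has less than a third of the men the SAP requires. The documents support neither step. The 102 fits both scales and may count screened men. It also belongs to the dropped 1:2 contrast; with equal allocation the relative effect needs about 130 to 133 threshold-meeting men per arm.

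The superseded adherence row does lean towards relative. A 20% relative rise in MPR (0.12) needs 1.5 × 7.849 × 0.35²/0.12² = 100.2 men, and 100.2/(0.25 × 0.715) = 560, the printed number per arm. But 100.2/(0.25 × 0.70) = 572, using that table's 70% screening rate, is also close, so this does not settle the scale.

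Nor is 60 a ceiling. Panels exceed 100 eligible men, outcomes are to be assessed in all eligible patients, and new patients replace leavers. The 60 follows from Table 6's basis of 100 per team, which is the basis on which the power is stated.

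**Conclusion.** The concern holds as a defect of support. The treatment row omits the scale of the increase, the number of men analysed and the ICC. At the table's own rates, above 0.99 is not reached on either scale with one year of usual-care screening (30 men). It is reached only if the increase is absolute, usual-care screening accrues over two years, and there is little or no clustering. On the relative reading, power is about 0.36 to 0.72 and the over-85% summary fails for this endpoint in every case examined. On the absolute reading, that summary holds.

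These figures rest on 100 men per team, Table 6's screening and threshold rates, an ICC from 0 to 0.1, and a normal-approximation comparison of two proportions without covariate adjustment. The documents do not establish which scale was meant.

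**What to change.** In the protocol's Table 6 and the matching table in the SAP's Revised Analysis Plan:
- State whether the 30% increase is relative (to 71.5%) or absolute (to 85%). The sponsor should say which was intended; it should not be inferred from the superseded table.
- Give the expected number of screened, threshold-meeting men per arm (about 30 to 60 vs 190 to 380 on present assumptions), the accrual period assumed and the ICC used.
- Replace the figure above 0.99 with power recomputed on those inputs.
- If the relative scale is meant, qualify the over-85% sentence so that it no longer covers initiation.

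The cost is wording and one recalculation. No extra patients are needed. The only downside is a stated power that may look less favourable.
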